7.4. Electrocardiogram

Triplicate 12-lead ECGs will be obtained as outlined in the Schedule of Activities. An average of the 3 consecutive ECG values for each parameter (heart rate, PR interval, QRS interval, QT interval, and QTc interval), or 1 or 2 values if all 3 are not available, will be used for generating the summary statistics. Descriptive statistics for ECG parameters and their changes from baseline at each assessment time point will be presented by treatment group. QTc interval will be calculated using Fridericia correction ($QTcF=QT/(RR)^{1/3}$); if RR is not available, it will be replaced with 60/hr in the correction formula. ECG interpretation (designated as normal, abnormal not clinically significant, abnormal clinically significant) will be summarized by time point. A shift table from baseline to each visit for qualitative ECG results will be presented and all the data will be listed.

In addition, the number and percentage of subjects with PCS postbaseline ECG results will be tabulated by treatment group (or cohort). An ECG value will be considered PCS if it meets the observed value criterion. The criteria for PCS ECG values are detailed in [Table 5](#). The percentages will be calculated relative to the number of subjects with available non-PCS baseline values and at least 1 postbaseline assessment. The potential numerator will be the total number of subjects with available non-PCS baseline values and at least 1 postbaseline PCS value in the corresponding postbaseline period.

A supportive data listing for subjects with PCS postbaseline values will be provided, including the subject ID number, baseline and postbaseline values for each visit, and a flag indicating the PCS ECG values.

Table 5: Criteria for Potentially Clinically Significant ECG Values

ECG Parameter	Unit	Higher Limit
QRS Interval	msec	≥ 150
PR Interval	msec	≥ 250
QTc Interval	msec	> 500

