12. Subject has a 12-lead ECG demonstrating severe bradycardia (heart rate <40 beats per minute) or average QTcF \geq 450 msec for males and \geq 470 msec for females at the Screening Visit or at Check-in on Day -1.
13. Subject has elevated (>1.5 times the upper limit of normal as defined by the laboratory) levels of alanine aminotransferase (ALT), aspartate aminotransferase (AST), creatinine, or bilirubin at the Screening Visit or at Check-in on Day -1.
14. Subject has confirmed or suspected infection with SARS-CoV-2 (COVID-19) at the Screening Visit or Check-in on Day -1, or was diagnosed with COVID-19 or had contact with a person with COVID-19 within 14 days of the Screening Visit.
15. Subject has positive serology for human immunodeficiency virus (HIV)-1, HIV-2, or hepatitis B surface antigen (HBsAg), or positive for anti-HIV-1, anti-HIV-2, or anti-hepatitis C virus (HCV) antibodies at the Screening Visit.
16. Identification of an anatomical abnormality upon Screening rectal examination which will make enema administration difficult.

Other Exclusions

17. Subject has a history of difficulty receiving an enema.
18. Subject has a history of alcohol or drug addiction during the year before the Screening Visit, or has a positive drug or alcohol screen at the Screening Visit or Check-in on Day -1.
19. Subject has ingested any alcohol-containing foods or beverages during the 48 hours before Check-in (Day -1). Ingestion of alcohol-containing foods or beverages is excluded during the study until after the Follow-up Phone Call on Day 21.
20. Subject has donated blood products during the 6 weeks before Check-in (Day -1).
21. Subject is involved in the conduct and administration of this study as an investigator, subinvestigator, study coordinator, other study staff, or sponsor staff.

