7.3. Vital Signs

Descriptive statistics for body weight and vital signs (ie, oral temperature, supine systolic and diastolic blood pressure, and pulse) and changes from baseline values at each time point will be presented by treatment group, and all the data will be listed. If there are multiple measurements for the same time point, the first one will be used for the by-time point analysis.

The number and percentage of subjects with PCS postbaseline vital signs will be tabulated by treatment group (or cohort). A vital sign value will be considered PCS if it meets both the observed value criterion and the change from baseline criterion. The criteria for PCS vital sign values are detailed in [Table 3](#). The PCS percentages will be calculated relative to the number of subjects with baseline values and at least 1 assessment in the postbaseline period. The numerator will be the total number of subjects with available baseline values and at least 1 postbaseline PCS value.

A supportive data listing for subjects with PCS postbaseline values will be provided, including the subject ID number, baseline and postbaseline values for each visit, and a flag indicating the PCS vital sign values.

Table 3: Criteria for Potentially Clinically Significant Vital Signs

Vital Sign Parameter	Flag	Criteria ^a	
		Observed Value	Change from Baseline
Supine systolic blood pressure (mmHg)	High	≥180	Increase of ≥20
	Low	≤90	Decrease of ≥20
Supine diastolic blood pressure (mmHg)	High	≥105	Increase of ≥15
	Low	≤50	Decrease of ≥15
Supine pulse (beats per minute)	High	≥120	Increase of ≥15
	Low	≤50	Decrease of ≥15
Weight (kg)	High	-	Increase of ≥7%
	Low	-	Decrease of ≥7%

^a A postbaseline value is considered as a PCS value if it meets the criteria for both observed value and change from baseline.

In addition to supine measurements, at the predose measurement and at various postdose time points on days 1, 2, 7 and 8, standing blood pressure and pulse will be measured 3 minutes after the supine measurements are taken. The change in blood pressure from supine to standing, along with associated adverse events, will be used to assess orthostatic hypotension. The criteria for testing positive for orthostatic hypotension are presented in [Table 4](#).

Table 4: Criteria Associated with Orthostatic Hypotension

Blood Pressure Parameter	Blood Pressure Change from Supine to Standing
Systolic blood pressure (mmHg)	Decrease of ≥20 mmHg
Diastolic blood pressure (mmHg)	Decrease of ≥10 mmHg

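### The ECG flag table in SAP 7.4 uses only absolute upper limits, so it does not count QTcF between the entry limits and 500 msec, large rises ending at or below 500, or any heart rate

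*SAP*

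**What the plan says.** SAP 7.4 averages each triplicate for five parameters: "heart rate, PR interval, QRS interval, QT interval, and QTc interval". It plans three kinds of output:

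- Numeric summaries: "Descriptive statistics for ECG parameters and their changes from baseline at each assessment time point will be presented by treatment group". SAP 11.1.1 defines descriptive statistics as n, mean, median, SD, minimum and maximum.
- The site's interpretation (normal, abnormal not clinically significant, abnormal clinically significant) by time point, with a shift table from baseline and a full data listing.
- A PCS count and a supporting listing, with this rule: "An ECG value will be considered PCS if it meets the observed value criterion". Table 5 gives QRS ≥150, PR ≥250 and QTc >500 msec. The denominator is subjects with a non-PCS baseline and at least one postbaseline ECG.

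For vital signs, SAP 7.3 has a different rule: "A vital sign value will be considered PCS if it meets both the observed value criterion and the change from baseline criterion". Table 3 flags low supine pulse at ≤50 bpm with a fall of ≥15, and flags weight on percentage change alone.

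Protocol 5.2, exclusion 12, bars a subject whose ECG at Screening or Check-in is one "demonstrating severe bradycardia (heart rate <40 beats per minute) or average QTcF" of at least 450 msec (males) or 470 msec (females). SAP 7 takes the average of the last predose triplicate as the numeric ECG baseline.

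**The concern.** Safety and tolerability is the primary objective, and the Protocol synopsis says the data will be used to enable a Phase 2 study. Triplicate ECGs are taken before and 2 h after each of seven doses. The PCS table is the only planned output that applies numeric thresholds to them subject by subject. Its QTc limit lies well above the range in which eligible subjects start, it does not look at change, and it omits heart rate although heart rate is one of the parameters summarised. A row of zeros could be read as showing that no subject had a notable QTcF or heart-rate value, when the table was not built to detect such values below its limits.

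**Working it through.** The plan gives no figure to reproduce, because no sample-size calculation was done. The check compares thresholds.

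**Inputs.** Table 5: QTc >500 msec, no heart-rate row (SAP 7.4). Entry limits: 450 and 470 msec, heart rate 40 bpm (Protocol 5.2). Pulse flag: ≤50 bpm and a fall ≥15 (SAP Table 3). ECG and vital-sign times: Schedule of Activities and Protocol 8.2.2. Six active and three placebo subjects per cohort (SAP 4.1.1).

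**1. QTcF range not flagged.** From the entry limit up to and including 500 msec: 450–500 in males (width 500 − 450 = 50) and 470–500 in females (width 500 − 470 = 30).

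**2. Rise needed for a flag.** The rise must exceed 500 − baseline.

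| Baseline QTcF (msec) | Rise must exceed (msec) | Flagged after +60? |
|---|---|---|
| 400 | 100 | No (460) |
| 420 | 80 | No (480) |
| 440 | 60 | No (500 is not >500) |
| 449 (male just under the limit) | 51 | Yes (509) |
| 469 (female just under the limit) | 31 | Yes (529) |

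A subject who goes from 400 to 480 msec enters neither the count nor the PCS listing.

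**3. How often a 60-msec rise could be flagged.** It needs a baseline above 500 − 60 = 440 msec. The documents give no QTcF distribution, so I assume normal baselines truncated at the entry limit, with share = [F(limit) − F(440)] / F(limit). For mean 390 and SD 15 the share is 0.04% in both sexes. For mean 400 and SD 20 it is 1.7% of males and 2.3% of females. For mean 415 and SD 20 it is 6.8% and 10.3%.

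**4. Heart rate.** Table 5 can flag no value. The Table 3 pulse rule gives partial cover:

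- Pulse 35 from a baseline of 50: fall 50 − 35 = 15, flagged.
- Pulse 39 from 54: fall 54 − 39 = 15, flagged.
- Pulse 39 from 53: fall 53 − 39 = 14, not flagged.

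Pulse and ECG are both scheduled at 2 h postdose on Days 1 and 7. On Days 2–6 pulse is scheduled predose only, while the ECG is also taken 2 h postdose. Those five postdose heart rates per subject come only from the ECG.

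**5. Number of triplicates.** 2 per dosing day × 7 days = 14. The Day 1 predose set is the baseline, leaving 14 − 1 = 13 postbaseline.

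**6. What the group summaries show.** One rise of 80 msec among six subjects moves the group mean by 80 / 6 = 13.3 msec, if the other five do not change. The maximum change at that time point would be at least +80. The maximum does not say how many subjects had a large rise, or whether the maxima at different time points belong to the same subject.

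**The case against.** The strongest reply is that the extremes are already reported. Because descriptive statistics include minimum and maximum, the largest QTcF rise and the lowest heart rate in each arm appear at every time point. This stands, and it defeats any claim that marked rises are hidden in means. All ECG data are also listed, for at most 27 subjects. ECG abnormalities that the investigator judges clinically significant are adverse events (Protocol 10.3.1.3), and the Dose Escalation Committee reviews ECGs before further cohorts. What these outputs lack is a count of subjects against a numeric limit or change across the 13 triplicates.

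A reader might go further in four ways that the documents do not support:

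- *Table 5 contradicts the protocol.* It does not. An entry limit serves eligibility, and nothing says it defines a PCS value after dosing.
- *The table will read zero for any plausible drug effect.* The documents give no expected effect on QTcF, and any value above 500 msec is flagged, including a rise that ends there.
- *It is the only categorical ECG output.* The interpretation summary and shift table are also categorical and do not depend on the 500-msec limit.
- *The ECG rule is an anomaly within the SAP, and the vital-sign rule should be copied.* The laboratory flags in Table 2 also use observed values only. Table 3 requires both criteria for blood pressure and pulse, so copying it would make the ECG flag harder to meet. Only its weight row is a stand-alone change criterion.

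**Conclusion.** The gap is real and modest. The PCS count and listing are insensitive to QTcF from the entry limits up to 500 msec, to large rises that end at or below 500, and to any ECG heart rate. From an assumed baseline of 400–420 msec, a subject must rise by more than 80–100 msec to be counted. From just under the entry limits the rise is a little over 50 msec (males) or 30 msec (females). These findings rest on the documents' own thresholds. Only the 400–420 msec baseline and the shares in step 3 are assumptions, and the conclusion does not depend on those shares. No data are lost, and the incidence of TEAEs and TESAEs is counted as before. Other outputs partly cover the gap but do not give the per-subject count. The case for changing the table is that the data and the baseline already exist.

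**What to change.** Before database lock, extend SAP Table 5 with:

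- **QTcF categories below 500 msec**, for example at the protocol's entry limits by sex (≥450 males, ≥470 females). Keep the present denominator of subjects not PCS at baseline. Entry is judged at Screening and Check-in, so a Day 1 predose baseline could already lie above the limit.
- **A stand-alone QTcF change category**, for example increases of >30 and >60 msec. These two values are proposals, not figures from the documents, and the sponsor should confirm them. The denominator is all subjects with a baseline and at least one postbaseline value.
- **A heart-rate row**, for example <40 bpm as in exclusion 12, again with the non-PCS-at-baseline denominator.

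Extend the supporting listing to the same criteria. These are reporting categories only; they add no assessments and do not alter subject management. The cost is SAP wording and programming. The downside is a few flags from ordinary variability, to be read against pooled placebo.

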7.5. Bladder and Bowel Movement Diary (BBMD)

The analysis of the bladder and bowel movement diary (BBMD) parameters will be based on the Safety Analysis Set. Subjects will enter BM-related information into a paper diary, the BBMD, on an event-driven basis (ie, following each BM) during the Screening Period (beginning at Day -8) and throughout the Clinic Period. The BM related information will include the day and time of BMs and a report of stool consistency for each BM using the Bristol Stool Form Scale (BSFS) (1=Separate hard lumps like nuts [difficult to pass], 2=sausage shaped but lumpy, 3=like a sausage but with cracks on surface, 4=like a sausage or snake, smooth and soft, 5=soft blobs with clear-cut edges (passed easily), 6=fluffy pieces with ragged edges, a mushy stool and 7=Watery, no solid pieces [entirely liquid]).

Subjects will complete the bladder portion of the BBMD in the morning of Dosing Day 1 (which represents the baseline responses) and each subsequent morning from Dosing Day 2 thru Discharge Day 8. The bladder diary will include the following questions:

In the past 24 hours...

- Did you have to urinate more frequently than normal? (yes/no)
- How many times did you urinate? (0 to 2; 3 to 6; 7 to 10; or more than 10)
- Did you feel the strong need to urinate with little or no warning? (yes/no)
- Did you have to get up to urinate during the night more frequently than usual? (yes/no)
- How many times did you have to get up at night to urinate? (0, 1, 2, 3+ times)
- Did you have pain or burning in your bladder or pelvic area? (yes/no)

7.5.1. BBMD Analysis

BM data will be summarized by treatment for the baseline period and for the post-baseline period covered by the $7 \times 24 = 168$ hours after the first dose of study drug using descriptive statistics. Change from baseline for the following BM parameters will be calculated:

- BM frequency
- Stool consistency (BSFS)

The baseline period for BM data is exactly 1 week and consists of the seven 24-hour periods that end at the time of first dose. Baseline values will be derived from the BBMD data collected during that period. The baseline BM daily frequency rate (BMs per day) will be calculated as the number of BMs the subject reports during this period divided by 7. Baseline stool consistency will be calculated as the average of the non-missing BSFS scores associated with the BMs reported by the subject during this period.

For BM data, the postdosing frequency and averages will be based on events and reports that occur during the seven 24-hour periods that start on Day 1 at the time of dosing and end on Day 8. Change from baseline will be defined as the postdosing values minus the baseline value. The data will be provided in listings as well.

The data regarding bladder symptoms and urination is categorical. The baseline values are simply the responses to the 6 relevant questions asked, predose, in the morning of Dosing Day 1, and the postdosing values are the responses to the BBMD on Days 2 through 8.

For the bladder symptoms and urination data, shift tables by study day will be created for each of the 6 questions, showing the responses for the 24 hours before dosing (completed on the morning of dosing, Day 1) versus the responses for the seven postdose 24-hour periods.

For the Day 1 pre-dosing Bladder and Urination data, summary analyses will only include diaries that were completed before dosing. Any diaries that were completed after the first dose will not be used. Similarly, for the Day 2 Bladder and Urination diary, only diaries that were completed between 20 and 32 hours after dosing will be used, to avoid overlap with pre-dosing and with Day 3. A similar 12 hour window will be used for the BBMD diaries for days 3 through 8.

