1.3. Schedule of Activities

Table 1: Schedule of Activities

Study Period→		Screening Period	Clinic Period					Follow-up Period
Study Procedure↓	Visit/Day→	Screening Visit Day -36 to Day -8	Check-in Day -1	Dosing Day 1	Days 2 through 6	Day 7	Discharge Day 8 ^{a/} ET	Follow-up Phone Call Day 21 (+3 days)
Informed consent		X						
Eligibility criteria		X	X					
Medical history		X						
Demographics		X						
Body weight & height ^b		X		Pre			X	
Urine drug & alcohol screen		X	X					
Physical examination ^c		X	X	Pre	Pre	Pre	X	
Rectal examination ^d		X	X	Pre	Pre	Pre	X	
Vital signs ^e		X	X	Post: 0.5, 2, 4, and 8h ($\pm 10m$) Pre: 0 ($\leq 25m$)	Days 3 through 6 Pre: 0 ($\leq 25m$)	Post: 0.5, 2, 4, and 8h ($\pm 10m$)		
Orthostatic blood pressure and pulse ^f				Pre: 0 ($\leq 25m$) Post: 1 and 6h ($\pm 20m$)	Day 2 only Pre: 0 ($\leq 25m$)	Pre: 0 ($\leq 25m$) Post: 1 and 6h ($\pm 20m$)	24h post-Day 7 dose ($\pm 20m$)	
TriPLICATE 12-lead ECG ^g		X	X	Pre: 1h ($\pm 30m$) Post: 2h ($\pm 30m$)	Pre: 1h ($\pm 30m$) Post: 2h ($\pm 30m$)	Pre: 1h ($\pm 30m$) Post: 2h ($\pm 30m$)		

Study Period→		Screening Period	Clinic Period					Follow-up Period
Study Procedure↓	Visit/Day→	Screening Visit Day -36 to Day -8	Check-in Day -1	Dosing Day 1	Days 2 through 6	Day 7	Discharge Day 8 ^{a/} ET	Follow-up Phone Call Day 21 (+3 days)
Clinical chemistry, hematology, urinalysis		X	X	Pre: 0 (\leq 15m, \leq 30m for UA) Post: 6h (\pm 30m)	Day 4 only Pre: 0 (\leq 15m, \leq 30m for UA)		X	
ESR and CRP blood draw ^h			X				X	
FSH		X						
HCG ⁱ		X	X					
SARS-CoV-2 testing		X	X					
HIV & hepatitis panel		X						
BBMD training		X						
BBMD dispensed		X	X					
Daily BBMD completion ^j	Day -8 through Day -2	X		X	X	X	X	
BBMD collection and review ^k			X				X	
Concomitant medications		X	X	X	X	X	X	X
AE monitoring		X	X	X	X	X	X	X
Subject confinement to clinic ^l			X	X	X	X	X	
Start of predose fast ^m				Pre: \geq 6h	Pre: \geq 6h	Pre: \geq 6h		
Randomization				X				

Study Period→		Screening Period	Clinic Period					Follow-up Period
Study Procedure↓	Visit/Day→	Screening Visit Day -36 to Day -8	Check-in Day -1	Dosing Day 1	Days 2 through 6	Day 7	Discharge Day 8 ^a / ET	Follow-up Phone Call Day 21 (+3 days)
Study drug administration ⁿ				X	X	X		
PK blood draws ^o				Pre: 0 (≤ 15 m) Post: 0.5 (± 2 m), 1, 2, 4, 6, and 8h (± 20 m)	Pre: 0 (≤ 15 m)	Pre: 0 (≤ 15 m) Post: 0.5 (± 2 m), 1, 2, 4, 6, and 8h (± 20 m)	24h post- Day 7 dose (± 20 m)	

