4.1.1. Study Periods

4.1.1.1. Screening Period

The Screening Period will begin with the signature of the informed consent form (ICF) at the Screening Visit (which can occur from Day -36 to Day -8) and will last 7 to 35 days. At the Screening Visit, subjects will undergo preliminary screening procedures to ensure that they meet the inclusion and exclusion criteria for the study. Eligible subjects will receive the BM portion of the bladder and bowel movement diary (BBMD), a paper-based diary to complete on an event-driven basis (ie, for each BM) at home, and training on how to complete it to record their bowel habits. Subjects will complete the BM portion of the BBMD daily only for the 7 days before

Check-in on Day -1. The end of the Screening Period will coincide with the beginning of the Clinic Period at Check-in (Day -1).

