9.4.5. Safety Analyses

All safety analyses, including the BBMD analyses, will be based on the Safety Analysis Set.

Summaries for the safety parameters corresponding to the primary endpoints (including TEAEs and TESAEs) are described in Section 9.4.2. Additionally, listings will be provided for severe AEs, drug-related AEs, SAEs, and AEs leading to study discontinuation.

Descriptive statistics and changes from baseline at each assessment timepoint will be presented by treatment (or cohort) for the Clinic Period for:

- Clinical laboratory values (in standard units) for each hematology, chemistry, inflammatory marker, and urinalysis parameter
- Vital signs (ie, pulse rate, systolic and diastolic blood pressure, oral temperature, and body weight)

- ECG parameters (ie, heart rate and measures of PR, QRS, QT, and QTcF intervals)
 - Additionally, the overall 12-lead ECG interpretation (normal, abnormal not clinically significant, or abnormal clinically significant) will be summarized.

For the BBMD parameters, descriptive statistics at each assessment timepoint will be presented by treatment (or cohort) for each study period (Screening Period and Clinic Period): BM frequency, stool consistency, fecal incontinence, urinary frequency, urinary urgency, nocturia, and bladder/pelvic pain.

BM-related baseline values will be derived from the BBMD data collected in the Screening Period, specifically, the period of time from 7 days prior to Check-in up to the time of randomization on Day 1. Bladder-related baseline values will be derived from the BBMD data collected predose on Day 1 (with a 24-hour recall). The Clinic Period BM- and bladder-related values will be derived from the BBMD data collected after randomization in the Clinic Period, specifically, the period of time from Day 1 (postrandomization) through Day 8 (Discharge).

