11.4. Bladder and Bowel Movement Diary

Protocol C3300-102

SCREENING PERIOD

Subject Number: 001 - _____

Study Visit: _____ Date: _____, _____
Day of the week Month Day Year

BLADDER AND BOWEL MOVEMENT DIARY

Bowel Movements									
Did you have a Bowel Movement today?  Yes  No									
If yes, please complete the table below.									
Please complete one row below for each bowel movement (BM) . If you have more than one BM in a day, please complete additional rows as needed. At the end of each day, please confirm that all BMs for that day have been entered and complete a row for each BM you may have forgotten to record.									
Time of Bowel Movement	Describe the bowel movement form (Please refer to the Bristol Stool Form Scale)						Initials		
: _____  AM  PM	Type:	 1	 2	 3	 4	 5	 6	 7	
: _____  AM  PM	Type:	 1	 2	 3	 4	 5	 6	 7	
: _____  AM  PM	Type:	 1	 2	 3	 4	 5	 6	 7	
: _____  AM  PM	Type:	 1	 2	 3	 4	 5	 6	 7	
: _____  AM  PM	Type:	 1	 2	 3	 4	 5	 6	 7	
: _____  AM  PM	Type:	 1	 2	 3	 4	 5	 6	 7	

Bladder and Urination – Not Applicable for Screening

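### SAP 7.5.1 divides baseline bowel movements by a fixed 7, so an unrecorded diary period counts as zero; the documents also give three baseline windows and conflict on whether Day -1 is recorded

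*SAP*

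**What the plan says.** **Rate.** SAP 7.5.1 states that the BM baseline "is exactly 1 week and consists of the seven 24-hour periods that end at the time of first dose". The daily rate is "the number of BMs the subject reports during this period divided by 7". The post-dose period is the 168 "hours after the first dose of study drug using descriptive statistics"; the divisor for the post-dose rate is not stated. The section restricts which bladder diaries are usable by their time of completion, but has no rule for a BM diary that is missing or incomplete.

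**Window.** The documents describe three bowel baselines:
- *Run-in days.* Protocol 4.1.1.1: "Subjects will complete the BM portion of the BBMD daily only for the 7 days before" Check-in on Day -1. The schedule of activities shows "Day -8 through Day -2", and footnote k uses those days for eligibility. Protocol 4.2 and SAP 4.2 both say that seven consecutive Screening days establish the bowel baseline.
- *Protocol 9.4.5.* "the period of time from 7 days prior to Check-in up to the time of randomization on Day 1".
- *SAP 7.5.1.* The 168 hours ending at first dose.

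**Day -1.** The row for daily diary completion is blank at Check-in in Protocol Table 1 and in SAP Table 7. Yet Protocol 4.1.1.2 starts the Clinic Period on Day -1 and has event-driven BM entry continue in it. SAP 7.5 has recording throughout the Clinic Period, and the clinic diary form in SAP 11.4 is labelled for Day -1 to Day 8.

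**Form.** Both diary pages in SAP 11.4 ask, with a yes/no answer, "Did you have a Bowel Movement today".

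**The concern.** A fixed divisor is correct only when all seven periods were recorded. Otherwise a missing period enters the rate as a true zero, the baseline falls, and change from baseline rises with no drug effect. Most of the baseline comes from a paper diary kept at home, so a missed day is foreseeable, and the form already holds the item that separates a day without a BM from a day without a record.

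Protocol 2.3.1 names diarrhea as a class effect of this mechanism and relies on BM frequency and stool consistency to watch for it. Change from baseline in BM frequency is a planned safety output, summarized in groups of 6 active subjects.

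The error can also run the other way. If 7 is used after dosing as well, a subject who leaves the clinic early has an understated post-dose rate, which could hide a rise. SAP 6.1 expects that some subjects may withdraw before the Clinic Period ends.

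Finally, with three baseline definitions, the programmer must choose which days count, and one of the candidate days may have no diary.

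**Working it through.** **1. Window length.** 7 × 24 = 168 hours, which reproduces the SAP's post-dose figure and equals its one-week baseline.

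**2. Effect of the fixed divisor.** Let r be the true rate in BM/day and m the number of unrecorded 24-hour periods. The expected SAP baseline is r × (7 − m)/7. With no true change and a fully recorded post-dose period, the false rise is r × m/7. The range of r comes from inclusion criterion 3: 3 per week (3/7 = 0.43 per day) to 3 per day.

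| True rate (BM/day) | SAP baseline, m = 1 | False rise, m = 1 | False rise, m = 2 |
|---|---|---|---|
| 0.43 | 0.37 | +0.06 | +0.12 |
| 1 | 0.86 | +0.14 | +0.29 |
| 3 | 2.57 | +0.43 | +0.86 |

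One missing period gives 6/7 = 0.857 of the true rate (14% too low), and the post-dose rate then looks 7/6 = 1.17 times baseline. Two missing periods give 5/7 = 0.714 (29% too low).

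**3. Effect on a group mean.** One affected subject among 6, with one missing period, moves the mean change by 0.143/6 = 0.02 BM/day at 1 BM/day, and by 0.429/6 = 0.07 at 3 BM/day.

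**4. The windows side by side.** The documents say only that dosing is in the morning, so assume 09:00, with 06:00 to 12:00 as the range. There is no Day 0. The SAP window then contains:
- Day -8: 0 h
- Day -7: 15 h
- Days -6 to -2: 120 h
- Day -1: 24 h
- Day 1 before dosing: 9 h

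The sum is 168 h. The overlap with the run-in is 15 + 120 = 135 h, or 135/168 = 80% (132 to 138 h, 79% to 82%, over the range of dose times). The SAP drops all of Day -8 and part of Day -7, and adds Day -1 and the predose part of Day 1. If randomization falls at about the same clock time, the Protocol 9.4.5 window is 8.25 to 8.5 days, so a divisor of 7 does not fit it.

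**5. Day -1.** If h hours of Day -1 go unrecorded and BMs are spread evenly, the baseline is low by h/168. This is 0 if the whole day is recorded and 24/168 = 14% if none is. A gap before Check-in falls between these limits; the documents give no Check-in time.

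**6. After dosing.** If the divisor is 7 and only five periods are observed before withdrawal, the rate is 5/7 of the true rate, 29% too low. Counting calendar dates would not solve this. The 168 post-dose hours touch eight dates, Day 1 to Day 8, and dividing by 8 gives 7/8 = 0.875 of the true rate, 12.5% too low. The SAP's baseline window also touches eight dates, Day -7 to Day 1.

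**The case against.** Much can be said for the plan. Equal 168-hour windows on either side of the first dose are a coherent choice, and an analysis baseline need not equal the eligibility window. A reader might infer that dropping Day -8 is itself an error; the documents do not support that. Including Day -1 agrees with Protocol 9.4.5, which runs the baseline up to randomization.

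A reader might also infer from the blank schedule cell that Day -1 is never recorded, so that every arm will show a 17% rise. That is not supported either. Protocol 4.1.1.2, SAP 7.5 and the clinic form all provide for recording on Day -1, and both schedules dispense a diary at Check-in. The limit to seven days in Protocol 4.1.1.1 concerns the Screening diary. If Day -1 is recorded, this bias is zero; if it is not, all arms are affected alike and pooled placebo would show the shift.

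Nor is BM frequency the only quantitative evidence on diarrhea. Change in Bristol Stool Form Scale (BSFS) score is averaged over reported BMs, so the divisor does not touch it, and treatment-emergent adverse events are tabulated by grade. No hypothesis is tested.

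Missed diary days are foreseeable but not shown. The form asks for an end-of-day check, staff make a Day -9 reminder call where needed, and the diary is reviewed at Check-in.

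These arguments limit the consequence. They do not supply a missing-period rule, and they do not reconcile the windows.

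**Conclusion.** The concern holds in this form. SAP 7.5.1 states a rule that gives a wrong baseline whenever a period is unrecorded: 14% too low for one period, with a false rise of 0.06 to 0.43 BM/day for that subject. This assumes an unchanged true rate, BMs spread evenly over the week, and a complete post-dose record. Sporadic missed days and early withdrawal need not balance in groups of 6, although one affected subject moves a group mean only slightly (step 3).

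The three windows and the two accounts of Day -1 are contradictions in the text whatever the data turn out to be. The Day -1 bias is conditional: it arises only if that day, or the part before Check-in, goes unrecorded. The point is worth correcting before database lock. It does not put the study's descriptive safety conclusions in doubt by itself.

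**What to change.** 1. In SAP 7.5.1, compute baseline BM frequency as BMs reported divided by observed diary time in the window, in 24-hour periods (at most 7). Use the daily yes/no item to tell a true zero from a missing day.
2. State the same rule for the post-dose period. Count the partial Day 1 and Day 8 dates as fractions, so that 168 hours is never divided by 8, and truncate observed time at early withdrawal. If the baseline window ends at first dose, treat its partial first and last dates in the same way.
3. Use one baseline window in Protocol 9.4.5, SAP 4.2 and SAP 7.5.1, and align Protocol 4.2 with it. Either Days -8 to -2 or a window ending at first dose is workable. The first matches the run-in and needs no partial dates but no longer abuts dosing; the second abuts dosing but depends on Day -1.
4. If Day -1 is kept, mark daily diary completion at Check-in in both schedules and have BMs before Check-in that day recorded.

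The cost is a few lines of text and slightly more programming. The yes/no item is already on the form. Rates for subjects with missing periods will be less precise because they rest on less observed time.
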